### 7.2.7 Clinical Laboratory Evaluations

The following clinical chemistry, hematology, and urine parameters comprise the clinical laboratory evaluations:

Clinical chemistry	Sodium, chloride, potassium, bicarbonate (CO 2 ), magnesium, calcium, glucose, phosphate, total bilirubin (with direct and indirect fractionation, if total bilirubin is elevated >2 ULN), alkaline phosphatase, lactate dehydrogenase (LDH), aspartate aminotransferase (AST), alanine aminotransferase (ALT), albumin, total protein, creatinine, urea-nitrogen, uric acid, estimated glomerular filtration rate from the Cockcroft-Gault method, and, at Screening only, human chorionic gonadotropin (hCG) pregnancy test for women of child-bearing potential
Hematology	Hemoglobin, erythrocytes, hematocrit, mean corpuscular hemoglobin (MCH), mean corpuscular volume (MCV), mean corpuscular hemoglobin concentration (MCHC), leukocytes, differential blood count of neutrophils, eosinophils, basophils, monocytes, lymphocytes, and platelets.
Urinalysis	Qualitative analysis of glucose, ketones, nitrites, protein, pH, leukocytes, blood, bilirubin, specific gravity; microscopic examination for cells, casts, and bacteria  Urine pregnancy test for women of child-bearing potential. Performed at the site and results will be entered into the eCRF

Protocol Amendment #3 version: 22 February 2016

*This protocol is solely for the purpose of communicating information about the investigational drug between Insmmed Incorporated and study personnel. Information is not to be reproduced, abstracted or used for sharing of information for any other purpose, whatsoever, except with the written permission of Insmmed Incorporated.*

Other

Biomarkers CRP and IL-6

Assessments made only before the first administration of study drug are not considered safety parameters.

#### **7.2.7.1 Methodology**

Blood samples will be drawn with a minimum number of needle insertions to determine clinical chemistry and hematology parameters at Screening, and before administering study drug on Day 1, at Months 1, 3, 6, 8, and 12, and at EOT. Lab values that meet exclusionary criteria based on results from the central laboratory may be repeated at the Investigator's discretion and sent to the central laboratory provided that the re-evaluation is completed within the protocol defined Screening period and can only be repeated once. Only those labs that need to be re-evaluated should be performed as an unscheduled visit, not the entire laboratory panel. Details for collecting, handling, storing, and transporting blood samples will be provided in the site laboratory manual.

Urine samples will be collected at the same times as blood is drawn.

#### **7.2.7.2 Assessment**

Clinical chemistry and hematology analyses will be performed by a central laboratory; qualitative urinalyses will be performed by a central laboratory, and evaluated microscopically for cells, casts, and bacteria.

#### **7.2.8 Concomitant Medications**

The dosage of all concomitant medications should be recorded on the eCRF at every contact with a subject throughout the study period beginning with Day 1.

Protocol Amendment #3 version: 22 February 2016

*This protocol is solely for the purpose of communicating information about the investigational drug between Insmmed Incorporated and study personnel. Information is not to be reproduced, abstracted or used for sharing of information for any other purpose, whatsoever, except with the written permission of Insmmed Incorporated.*

Confidential

## **7.2.9 Audiology**

### **7.2.9.1 Methodology**

Audiology testing will be performed either at Screening or before administration of study drug at Baseline (Day 1), before study drug administration at Months 3, 6 and 12, and the end of treatment visit. Frequencies of 250, 500, 1000, 2000, 4000, and 8000 Hz will be evaluated for each ear using air conduction. If post-Baseline (Day 1) audiometry findings are an AE Grade 2 or higher (according to the Common Terminology Criteria for Adverse Events [CTCAE] Version 4.0 guideline), an additional audiometric evaluation should be conducted at the next scheduled visit.

### **7.2.9.2 Assessment**

Significant Baseline (Day 1) findings and all post-Baseline (Day 1) findings (including hearing loss of a CTCAE Grade 2 or higher) prior to first dose of LAI or multi-drug regimen on Day 1 must be recorded on the medical history page of the eCRF. Significant findings that meet the definition of an AE (including hearing loss of a CTCAE Grade 2 or higher) must be recorded on the AE page of the eCRF.

## **7.3 EXPLORATORY ENDPOINT VARIABLES**

### **7.3.1 St. George's Respiratory Questionnaire**

#### **7.3.1.1 Methodology**

The SGRQ is a self-administered questionnaire that has been validated in subjects with airways disease, specifically in subjects with BR (Jones 1991; Jones, et al. 1991; Wilson, et al. 1997). The SGRQ assesses health-related quality of life in subjects with chronic pulmonary disease by evaluating 3 health domains: symptoms (distress caused by respiratory symptoms); activity (effects of disturbances to mobility and physical activity); and impacts (the effect of disease on factors such as employment, personal control of one's health, and need for medication). The SGRQ will be completed before administration of study drug on Day 1, at Months 3, 6, 8, and 12, and at EOT and 3 months off-treatment.

Protocol Amendment #3 version: 22 February 2016

*This protocol is solely for the purpose of communicating information about the investigational drug between Insmmed Incorporated and study personnel. Information is not to be reproduced, abstracted or used for sharing of information for any other purpose, whatsoever, except with the written permission of Insmmed Incorporated.*

### **7.3.1.2 Assessment**

A composite total score is derived as the sum of domain scores for symptoms, activity, and impact, with 0 the best possible score and 100 the worst possible score. A reduction in score of 4 units is generally recognized as a clinically meaningful improvement in quality of life.

## **7.3.2 EQ-5D-3L**

### **7.3.2.1 Methodology**

The EQ-5D-3L, is a preference-based, (multi-attribute) generic health-status classification instrument that generates a composite score reflecting the preference value associated with a given health state. The system has 5 dimensions: mobility, self-care, usual activities, pain/discomfort, and anxiety/depression. Each dimension has 3 levels: no health problems, moderate health problems, and extreme health problems. Current general health is also scored using a visual analog scale. The EQ-5D-3L (Version 1.0 - 01Oct2014) will be completed before administration of study drug on Day 1, at Months 3, 6, 8, and 12, and at EOT and 3 months off-treatment.

### **7.3.2.2 Assessment**

The health state is reported with a 5-digit descriptor ranging from 11111, representing the best case, to 33333, representing the worst case. The score for each domain of the EQ-5D-3L will be reported in the eCRF.

## **7.3.3 Identification of New or Different MAC Strains**

### **7.3.3.1 Methodology**

In subjects who convert (i.e., who have 3 consecutive monthly negative MAC sputum cultures) and who subsequently have a positive MAC sputum culture, analyses will be conducted to confirm whether the positive MAC culture is due to a different MAC species or strain acquired by the subject, or due to a relapse of the same MAC species or strain as observed at Baseline (Day 1). The MAC species will be identified by sequencing the gene for the 16S rRNA subunit.

Protocol Amendment #3 version: 22 February 2016

*This protocol is solely for the purpose of communicating information about the investigational drug between Insmmed Incorporated and study personnel. Information is not to be reproduced, abstracted or used for sharing of information for any other purpose, whatsoever, except with the written permission of Insmmed Incorporated.*

If the MAC isolates identified after conversion are a different species, it will be determined that the subject acquired a different MAC species, rather than having a relapse. If the same species as seen at Baseline (Day 1) is observed, then DNA fingerprinting (based on a variable number of tandem repeat) will be conducted to identify the strain to determine whether the subject has acquired a different MAC strain.

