## 3 INVESTIGATIONAL PLAN

### 3.1 STUDY DESIGN

The Screening window allows time for sputum culture results, susceptibility by minimum inhibitory concentration (MIC) determination, and scheduling of Screening assessments. Any delay in obtaining microbiological results and MICs must be reported to the Sponsor immediately and documented within the study source documents. In the event that sputum culture results are not known by 8 weeks (Day -14), the Baseline (Day 1) visit should be scheduled as soon as possible in order to maintain the Screening window, and an extension of the Screening window to 14 weeks is allowed, if necessary. If sputum culture results are known prior to 8 weeks (Day -14), the Screening window of 10 weeks must be maintained. Once Screening assessments are complete and sputum culture results are known, eligible

Protocol Amendment #3 version: 22 February 2016

*This protocol is solely for the purpose of communicating information about the investigational drug between Insmid Incorporated and study personnel. Information is not to be reproduced, abstracted or used for sharing of information for any other purpose, whatsoever, except with the written permission of Insmid Incorporated.*

Confidential

subjects will be randomized 2:1 to LAI administered QD plus a multi-drug regimen or a multi-drug regimen alone. The primary endpoint will assess culture conversion by Month 6.

Sputum culture results will only be available to the site after the Month 6 sputum result is known, in time for the Month 8 visit. At Month 8 (-28 to +7 days), after all sputum culture results are known, up to and including Month 6, subjects will be assessed as converters or non-converters.

All converters will remain in Study INS-212 (Section 4.6). All converters who, after culture conversion, subsequently have MAC-positive sputum cultures in liquid broth media (agar negative) for 1 or 2 consecutive months only, will also remain in Study INS-212. These subjects will continue on their randomized treatment regimen until they complete a total of 12 months of treatment (EOT), starting from the first of 3 negative cultures that defines culture conversion. These subjects will return after the EOT visit for 28 day, 3, 6 and 12 months off-treatment follow-up visits. The 12 months off-treatment follow-up visit will be the end of study (EOS) visit. No NTM treatment will be administered during the off-treatment phase.

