## 4.1 INCLUSION CRITERIA

To be eligible for enrollment, a prospective patient must meet all of the following criteria:

1. be male or female, 18 years or older (20 years or older in Japan)
2. be positive for MAC on culture as defined in inclusion criterion No. 4 while being treated with a multi-drug treatment regimen (at least 2 antibiotics) for a minimum duration of 6 consecutive months that is either ongoing or was stopped no more than 12 months before Screening (exceptions to multi-drug treatment regimen for 6 consecutive months include treatment with doses or frequencies below those recommended by guidelines and/or short interruptions of therapy, both occurring due to safety/tolerability issues)
3. be diagnosed with MAC NTM lung infection with evidence of underlying lung disease such as nodular bronchiectasis and/or fibrocavitary disease by chest radiography or chest computed tomography. High resolution CT (HRCT) scan is preferred, if available
4. have a MAC lung infection documented by at least 2 positive cultures (MAC or mixed infection with MAC as the dominant species), consisting of at least one obtained within 6 months prior to Screening and one positive culture at Screening (cultures to be at least 1 month apart). Cultures may be obtained from sputum or bronchoscopy.
5. have a MAC-positive sputum at Screening
6. be willing to adhere to multi-drug treatment regimen during the course of the study
7. be able to produce approximately 3 mL of sputum or be willing to undergo an induction that produces approximately 3 mL of sputum for mycobacteriology
8. female of child bearing potential agrees to practice an acceptable method of birth control (e.g., true abstinence [refraining from heterosexual intercourse during the entire study], hormonal or barrier methods, partner sterilization, or intrauterine device [IUD]) while participating in the trial. Periodic abstinence (e.g., calendar, ovulation, symptothermal, post-ovulation methods), declaration of abstinence for the duration of the study, and withdrawal are not acceptable methods of contraception.

Protocol Amendment #3 version: 22 February 2016

*This protocol is solely for the purpose of communicating information about the investigational drug between Insmmed Incorporated and study personnel. Information is not to be reproduced, abstracted or used for sharing of information for any other purpose, whatsoever, except with the written permission of Insmmed Incorporated.*

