### **7.1.2 Microbiological Assessment**

Sputum specimens will be cultured in liquid media in addition to solid media (agar). If results are negative on agar, the liquid media will be held for 6 weeks before reporting as culture negative.

Standard antibiotic sensitivity testing using MICs will be routinely performed on bacterial isolates (Clinical and Laboratory Standards Institute [CLSI] M48-A and NCCLS M24-A)

Protocol Amendment #3 version: 22 February 2016

*This protocol is solely for the purpose of communicating information about the investigational drug between Insmmed Incorporated and study personnel. Information is not to be reproduced, abstracted or used for sharing of information for any other purpose, whatsoever, except with the written permission of Insmmed Incorporated.*

(Forbes 2008). All mycobacterial isolates will be banked for subsequent determination of amikacin susceptibility and selective molecular typing (Prammananan, et al. 1998).

Isolates of MAC will be identified to complex, using a commercial RNA probe (AccuProbe, Gen Probe, Inc.) and subsequently identified to species (*M. avium*, *M. intracellulare*, MAC “X” group) using molecular methodology (Cousins, et al. 1996).

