#### **12.4 USE OF STORED SAMPLES AND DATA**

Serum and sputum samples collected for PK analysis will be stored for a period of up to 2 years after the completion (termination) of the study, or longer if required by the institution participating in the study. Serum samples from the IL-6 analysis will be stored at the aforementioned laboratory for a period of up to 2 years after the completion (termination) of the study, or longer if required by the institution participating in the study to see whether there may be indicators associated with NTM lung infections and for other exploratory analyses for an NTM lung infection (no genetic testing or analysis will be performed on blood samples collected). Mycobacterial isolates will be stored for a period of up to 2 years after the completion (termination) of the study, or longer if required by the institution participating in the study and used for future selective susceptibility testing for correlation with microbiologic and clinical response and for molecular typing of serial isolates to look for multiple strains within individuals that might influence treatment outcome. Stored samples will be labeled with study and subject information and kept in a locked room with limited access. Electronic data will be kept in password-protected computers at the laboratory and then transferred to the Sponsor or Clinical Research Organization (CRO), as applicable, for data analysis. Samples and corresponding data will be tracked using the laboratory's specimen tracking system.

Prior Sponsor and IRB approval are required before using or sharing study samples or data in ways not specifically specified in the study protocol.

Any loss or unanticipated destruction of samples (e.g., freezer malfunction) or data (e.g., loss of a data sheet with individually identifiable information) that violates or compromises the scientific integrity of study data must be reported to the Sponsor and the IRB.

At any time, subjects may inform the Investigator that they do not wish to have their samples stored beyond the completion (termination) of the study. In this case, the Investigator will request that all known remaining samples be destroyed and report the disposition of samples to the requesting subjects and the IRB.

Protocol Amendment #3 version: 22 February 2016

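### New MAC strains are judged against the Day 1 isolate alone, so a strain found only at Screening counts as newly acquired and a Day 1-negative subject has no reference

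*Protocol*

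**What the plan says.** Protocol Section 7.3.3.1 applies to converters who later have a MAC-positive culture. The later isolate is attributed either to a different species or strain, "or due to a relapse of the same MAC species or strain as observed at Baseline (Day 1". Two rules follow:

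- If the species differs, "it will be determined that the subject acquired a different MAC species, rather than having a relapse".
- A matching species leads to a second step, at strain level: "If the same species as seen at Baseline (Day 1) is observed, then DNA fingerprinting" is carried out to decide whether the strain differs.

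Section 7.3.3.2 adds no other reference and no category for isolates that cannot be classified.

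Four other places bear on this rule:

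- **Section 4.1, eligibility.** Criterion 5 is to "have a MAC-positive sputum at Screening". Criterion 4 asks for two positive cultures, "consisting of at least one obtained within 6 months prior to Screening and one positive culture at Screening (cultures to be at least 1 month" between them. No criterion concerns the Day 1 result.
- **Section 3.1, timing.** The Screening window is 10 weeks, and "an extension of the Screening window to 14 weeks is allowed, if necessary".
- **Section 7.1.2, banking.** "All mycobacterial isolates will be banked for subsequent determination of amikacin susceptibility and selective molecular typing".
- **Section 12.4, stored isolates.** Planned uses include "molecular typing of serial isolates to look for multiple strains within individuals that might influence treatment outcome".

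The result feeds exploratory objective 9 (Section 2.3) and exploratory endpoint 9 (Section 3.4). Section 9.6.3 plans only a summary of incidence by arm.

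**The concern.** A single time point is weak evidence that a strain was absent before treatment. The protocol itself allows for several strains in one subject (Section 12.4), and Section 1.1.1 describes MAC as a joint infection of two species. If the strain that regrows was there before treatment but was not recovered on Day 1, the rule records an acquisition where the subject has relapsed.

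The rule also presupposes a Day 1 isolate. Subjects qualify on Screening, so some may be culture-negative on Day 1, and 7.3.3.1 does not say how to classify them.

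At stake is whether endpoint 9, and the relapse-versus-reinfection reading of positives after conversion, can be defended. The isolate that qualified the subject for the trial is banked but plays no part in the rule.

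**Working it through.** The protocol states no figure for this endpoint, so there is nothing to reproduce. The check is mainly a reading of the rule.

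**1. Is Day 1 really the only reference?** Yes. The section names Baseline (Day 1) for both the species and the strain comparison. Where the protocol means a Screening result to serve as Baseline it says so, as it does for the ECG in Section 7.2.5.2. It does not do so here.

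**2. Can Day 1 be negative in a randomized subject?** Yes. Section 4.1 requires positivity at Screening only. Section 3.6.1 asks evaluable subjects for a Day 1 culture result, not a positive one. Section 7.1.2 holds agar-negative broth for 6 weeks before it is reported negative, so a negative Day 1 culture is not known at randomization.

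**3. The rule applied to possible histories** (X, Y and Z are species or strains):

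| Screening | Day 1 | Month 2 | After conversion | 7.3.3.1 as written | Reference = Screening and Day 1 |
|---|---|---|---|---|---|
| X | X | any | X | relapse | relapse |
| Y, or X and Y | X | any | Y | acquired | relapse |
| X | negative | any | X | no rule | relapse |
| X | negative | any | Y | no rule | new |
| X | X | Z | Z | acquired | new |
| X (Y carried, missed) | X (Y missed) | any | Y | acquired | new (residual error) |

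The second to fourth rows are the defect. The last row shows what the wider reference cannot repair.

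**4. Who can be affected?** Only converters with a later positive culture. At the planning rates and sample size of Section 9.1:

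- LAI: 174 × 0.20 = 34.8 converters
- control: 87 × 0.05 = 4.35 converters

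Fewer than these are typed, because a later positive culture is also needed. With the arm as denominator, one misclassified subject moves incidence by 1/174 = 0.57 percentage points (LAI) or 1/87 = 1.15 percentage points (control).

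**5. What would a second time point add? (Illustration only.)** Let d be the chance that one visit recovers a co-existing strain. Assume d between 0.5 and 0.9, and independent visits; the documents support neither assumption.

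- Day 1 alone misses the strain with probability 1 − d: 0.50 to 0.10.
- Screening plus Day 1 both miss it with probability (1 − d)²: 0.25 to 0.01.

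These are chances of missing a strain that exists. They are not misclassification rates: a second strain must also be present, persist through conversion and be the one that regrows.

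**The case against.** The best defence concerns weight. Endpoint 9 is exploratory and summarized descriptively, with no test attached. Relapse or recurrence in Section 4.6 is defined by MAC growth regardless of strain, and Section 9.6.2 counts relapse as failure for sustainability and durability on that basis. A reader might infer that misclassification lets treatment failures escape as reinfections in the efficacy results. The documents do not support that. This part of the defence stands in full.

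Second, Section 7.1.1 asks for at least 2 and preferably 3 sputum samples per assessment, from patients with at least two earlier positive cultures. That makes a missed strain or a negative Day 1 less likely but does not exclude either.

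Third, banking and serial typing are already foreseen, and an analysis plan or laboratory manual could settle missing references. But 7.3.3.1 is not silent: it states a rule, and neither Section 7.1.2 nor Section 12.4 changes it.

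Two further inferences should be resisted:

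- **A fourfold bias between arms.** If the same share m of converters were mislabelled in both arms, false new strains would be 0.20m of the LAI arm and 0.05m of control. For an assumed m of 5% to 20%, that is 1.0% to 4.0% against 0.25% to 1.0%. But m is unknown, and the ratio of four comes from typing converters only, whatever the reference isolate.
- **Every positive month before conversion should join the reference.** Objective 9 counts strains developed during the study. A strain first acquired at Month 2 and seen again after conversion would then be treated as old, so over-counting would give way to under-counting. Nor would early converters benefit: conversion is dated to the first of the three negatives (Section 2.1), so a Month 1 converter has only Screening and Day 1.

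**Conclusion.** The point holds as a defect in a stated rule with limited reach. Section 7.3.3.1 counts as acquired any species or strain that was present at Screening but not recovered on Day 1, and it cannot classify a subject who was negative on Day 1. Both follow from the text without any numerical assumption.

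The consequence is confined to exploratory objective and endpoint 9 and to the relapse-versus-reinfection reading of later positives. Conversion, sustainability and durability are unaffected.

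The size cannot be estimated. The documents give neither the frequency of mixed strains nor that of negative Day 1 cultures, and the true number of errors could be nil. A reader might infer that new-strain incidence will certainly be overstated. What the text supports is narrower: where a strain present before treatment is missed on Day 1 and regrows, the error is towards calling it new. With about 35 and 4 converters at the planning rates, and fewer typed, a single such subject would be noticeable in a descriptive count.

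**What to change.** Amend Section 7.3.3.1 as follows:

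1. Call a post-conversion isolate new only if its species or its tandem-repeat (VNTR) pattern differs from all banked pre-treatment isolates of that subject, meaning Screening and Day 1. Run fingerprinting when the species matches any of these, not only Day 1.
2. Use the Screening isolate as the reference when Day 1 is negative.
3. Report the subject as indeterminate when no pre-treatment isolate can be typed.
4. Report matches to isolates from on-treatment months before conversion separately, and do not count them as old, so that the endpoint still answers objective 9.

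The culture from before Screening is left out because the protocol does not say that its isolate is held.

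The cost is a wording change and a few extra typings of banked isolates, only in converters with a later positive culture. No new sampling is needed. A co-existing strain missed at both Screening and Day 1 would still be called new, and the report should say so.
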